Below is a list of abbreviations that are used in this clinical report.

6MWD	6 Minute Walking Distance
ADC	Apparent Diffusion Coefficient
ADL	Activities Daily Life
AMI	Acute Myocardial Infarction
CA	Cardiac Arrest
CO	Cardiac Output
COPD	Chronic Obstructive Pulmonary Disease
CPC	Cerebral Performance Category
CPR	Cardiopulmonary Resuscitation
DMC	Data Safety Monitoring Board
DW-MRI	Diffusion Weighted MRI
ECMO	Extracorporeal Membrane Oxygenation
EEG	Electro-encephalography
FIO2	Fraction of inspired oxygen
GCS	Glasgow Coma Scale
GCP	Good Clinical Practice
IABP	Intra-aortic Balloon Pump
ICU	Intensive Care Unit
IVRS	Interactive Voice Response System
IV	Intravenous
IEC	Independent Ethics Committee
LCC	Leuven Coordinating Centre
LVEF	Left Ventricular Ejection Fraction
MAP	Mean Arterial Pressure
MRI	Magnetic Resonance Imaging
NSE	Neuron Specific Enolase
NSTEMI	Non-ST segment elevation myocardial infarction
OR	Odds Ratio
PAC	Pulmonary Artery Catheter
PCI	Percutaneous Coronary Intervention

PEEP	Positive End-expiratory Pressure
PPV	Pulse Pressure Variation
ROSC	Resume of Spontaneous Contractions
SSEP	Somatosensory Evoked Potential
STEMI	ST segment elevation myocardial infarction
SVO ₂	Mixed Venous Oxygen Saturation
SVV	Stroke volume Variation
TIA	Transient ischemic attack

1. SYNOPSIS

Classification: Academic, Investigator Initiated Trial

Protocol Version and Date: Version 4, 20 Jan 2017

Title of Study: Neuroprotective goal directed hemodynamic optimization in post-cardiac arrest patients: a randomized controlled trial (the NEUROPROTECT post-CA trial)

Participating country: Belgium

Study Centers: 2 (UZ Leuven and ZOL Genk)

Study Period: 3 years

Anticipated start: July 2015

Anticipated completion: May 2018

Objectives:

The **primary objective** of the trial is to assess whether or not a new goal directed hemodynamic optimization strategy can reduce cerebral ischemia in post-cardiac arrest (CA) patients as quantified by diffusion weighted MRI (DW-MRI) to be performed at day 4-5 with quantification of the percentage of ischemic voxels with an apparent diffusion coefficient (ADC) below 0.650 mm²/s.

Secondary efficacy outcomes:

- Cerebral performance category 3-5 at discharge from the ICU CPC 1: return to normal cerebral function and normal living
CPC 2: Disability but sufficient function for independent activities of daily life
CPC 3: severe disability CPC 4: Coma
CPC 5: Death
- Cerebral performance category 3-5 at 180 days post-CA (assessed by trial investigators that are unaware of the treatment assignment)
- SF36 questionnaire at 180 days post-CA (assessed by trial investigators that are unaware of the treatment assignment)
- Neurocognitive testing at discharge from the hospital
- Biomarkers: Neuron specific enolase (day 1-2-3-4-5)

- Functional testing: Activities Daily Life (ADL) and 6 minute walking distance (6MWD) at discharge from the hospital
- Renal function: creatinine day 1-2-3-4-5 and urinary output day 1-2- 3-4-5.
- Length of stay in the ICU
- Duration of mechanical ventilation
- Placement of tracheostomy

Safety outcomes:

- Incidence of life threatening arrhythmias during intervention period
- Incidence of new onset atrial fibrillation during intervention period
- Incidence of pulmonary congestion requiring diuretics during intervention period

Methodology: Prospective, multi-centre, interventional open label investigator driven randomized controlled trial. Randomisation will be stratified by the presence of an initial shockable rhythm.

Number of subjects planned: A total of 112 pts are planned for this study.

Anticipated duration of trial: 3 years from first patient entered to last patient randomized

Diagnosis and main criteria for inclusion and exclusion:

Inclusion criteria:

- Out-of-hospital CA of presumed cardiac cause irrespective of the presenting rhythm
- Unconsciousness (Glasgow coma scale < 8) at hospital admission
- Age \geq 18 years
- Sustained return of spontaneous circulation (ROSC) (=when chest compressions have not been required for 20 consecutive minutes)

Exclusion criteria:

- Suspected or confirmed intracranial bleeding or stroke
- Known limitations in therapy or Do Not Resuscitate-order
- Known disease compromising 180 day survival
- Known pre-CA cerebral performance category 3-4
- Previous stroke (TIA can be included)
- MRI incompatible cardiac or neurosurgical device

- Systolic blood pressure < 90 mmHg on norepinephrine > 1 mcg/kg/min).
- Open chest
- ECMO (extracorporeal membrane oxygenation)
- Pregnancy

Interventional hemodynamic optimization protocol: In patients randomized to receive the intervention, the target mixed venous oxygen saturation (SVO₂) will be between 65-75% and the target mean arterial pressure (MAP) is between 85-100mmHg. Fluid administration and hemodynamic support will be adjusted according to a flow chart in case SVO₂ or MAP are below or above the suggested targets on an hourly basis.

Duration of treatment: The study protocol will start at admission in the intensive care unit (ICU) and will last 36 hours.

Reference therapies, dose and mode of administration: In patients randomized to receive current standard of care, hemodynamic support will be at the discretion of the treating physician with a target MAP of 65mmHg.

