6.3. Selection of Study Population

All patients presenting or referred to the investigational site after being successfully resuscitated from out of hospital CA will be screened for enrolment. All patients will be expected to meet all inclusion and exclusion criteria before entering the study. Minor deviations to these criteria may be allowed with prior approval of the principle investigator of the study site.

6.3.1. *Inclusion Criteria*

The patient must meet the following criteria:

1. Out-of-hospital CA of presumed cardiac cause irrespective of the presenting rhythm
2. Unconsciousness (Glasgow coma scale < 8) at hospital admission
3. Age \geq 18 years
4. Sustained return of spontaneous circulation (ROSC) (=when chest compressions have not been required for 20 consecutive minutes)

6.3.2. *Exclusion Criteria*

Exclusion Criteria:

1. Suspected or confirmed intracranial bleeding or stroke
2. Known limitations in therapy or Do Not Resuscitate-order
3. Known disease compromising 180 day survival
4. Known pre-CA cerebral performance category 3-4
5. Previous stroke (TIA can be included)
6. MRI incompatible cardiac or neurosurgical device
7. Systolic blood pressure < 90 mmHg on norepinephrine > 1 mcg/kg/min).
8. Open chest
9. ECMO (extracorporeal membrane oxygenation)
10. Pregnancy

6.3.3. *Withdrawal of Patients from Therapy or crossover*

In the intervention (“Neuroprotect post-CA”) group, a reduction in vasopressor doses to maintain a MAP of 65mmHg is recommended if any of the pre-specified serious adverse events that were potentially related to an increased rate of vasopressor infusion occurs. These events include: major ventricular arrhythmia requiring life support, electrical or pharmacological cardioversion, poorly tolerated supraventricular arrhythmia and peripheral limb ischemia.

Treatment may also be discontinued if the legal representative withdraws their consent.

All patients who are withdrawn from study treatment will have safety assessments completed during the entire course of the study.

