6.4. Baseline Characteristics to be collected

Baseline characteristics to be collected:

- Informed Consent
- Compliance with the inclusion/exclusion criteria will be documented
- Age
- Gender
- Medical history (chronic heart failure, previous AMI, previous cardiac surgery, previous arrhythmia, arterial hypertension, diabetes mellitus, COPD, chronic kidney disease, stroke)
- Chronic medication
- Arrest Characteristics (Public vs private place, bystander witnessed, bystander CPR performed, presenting rhythm, time to ROSC)
- Admission Characteristics (MAP, PaCO₂, PaO₂, Lactate, pupillary reflex, corneal reflex, FIO₂, dose of norepinephrine and dobutamine)
- Cause of arrest (STEMI, NSTEMI, arrhythmogenic, hypoxic, unknown)
- Angiography performed (time in hospital, time in cathlab, time in ICU)
- PCI performed
- SOFA score

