6.5. Study treatments

6.5.1. Treatments Administered

In patients assigned to the intervention group, placement of an IABP will be considered in the catheterization laboratory if the dose of norepinephrine necessary to achieve a MAP of 65mmHg exceeds 0.5 mcg/kg/min. In patients assigned to the intervention group, a new generation pulmonary artery catheter (CCOmbo, Edwards life sciences) will be inserted. Other trial interventions will start immediately after ICU admission and a summary flow chart guiding the targeted interventions is presented in the figure below. In patients randomized to receive the intervention, the target mixed venous oxygen saturation (SVO₂) is between 65-75% and the target MAP is between 85-100mmHg. Arterial blood

gas analysis will be performed on an hourly basis by treating nurses and physicians during the first 36 hours after ICU admission. Calibration of the continuous SVO₂ monitor will be performed per 4 hours by a central venous blood gass. In the treatment protocol, we will include specific recommendations for uniform and homogeneous interventions across centres in response to changing hemodynamic variables.

	MAP < 85 mmHg	MAP 85-100 mmHg	MAP > 100 mmHg

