6.6.3. Hourly manual recordings

- **All patients:**
 - o Blood gas analysis with determination of pH, p_aCO_2 , p_aO_2 , hemoglobin and lactate
 - o Adverse events:
 - Incidence of life threatening arrhythmias
 - Incidence of new onset atrial fibrillation
 - Incidence of pulmonary congestion requiring diuretics
 - Presence of limb ischemia
 - o If applicable
 - IABP ratio
 - Temporary pacing (Beats per minute)
- **Intervention group:**
 - o SVO_2 by blood gas per 4 hours to calibrate the continuous SVO_2 monitor

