#### **7.4 Methods for Withdrawals, Missing Data and Outliers**

For the primary endpoint, multiple imputation methodology will be used to account for missing data. A total of 100 imputations will be done. The imputation model will include the following:

Age, gender, presence of bystander CPR, presence of initial shockable rhythm, neuron specific enolase at days 1-2-3-4-5, presence of a malign EEG pattern on Day 1 and allocated treatment and death within 7 days of randomisation.

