## 10 Primary and Secondary Endpoints

### 10.1 Primary Endpoint

The primary endpoint will be summarised by randomised treatment group.

Since it is expected that a substantial proportion will have missing data for the primary endpoint (due to early mortality or other reasons), a statistical analysis that does not take account of this missingness is very likely to be subject to considerable bias.

Therefore, missing primary endpoint data will be imputed using the imputation model described in section 7.4.

In each imputation sample, the data will be analysed using an ANOVA that includes a factor for randomised treatment and the stratification factor of shockable rhythm. The results of the analyses will then be combined with standard methodology, using SAS PROC MIANALYZE.

The effect of randomised group will be estimated by the difference between groups and presented along with its associated 95% confidence interval.

The statistical analysis of the primary endpoint will be performed for the FAS and PPS.

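### The imputation model for the primary MRI endpoint has no measure of circulatory severity, although admission lactate, norepinephrine dose, MAP and SOFA are collected

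*Protocol*

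**What the plan says.** - **Who is enrolled.** Protocol Synopsis and 6.3.2 exclude "Systolic blood pressure < 90 mmHg on norepinephrine > 1 mcg/kg/min". Both conditions must hold. ECMO and open chest are also excluded. Lesser shock is eligible, and Protocol 6.5.1 foresees patients who need more than 0.5 mcg/kg/min of norepinephrine to reach a MAP of 65 mmHg.
- **Expected missingness.** SAP 10.1 anticipates that "a substantial proportion will have missing data for the primary endpoint (due to early mortality or other reasons"), and says that an analysis ignoring this would very likely be considerably biased. No rate is given.
- **Imputation model.** SAP 7.4 specifies 100 imputations from age, sex, bystander CPR, initial rhythm, NSE on days 1 to 5, and malign EEG on day 1, together with "allocated treatment and death within 7 days of randomisation". The list in Protocol 6.9.3 differs somewhat (it adds duration of advanced life support and outcome at ICU discharge), but it has no circulatory variable either.
- **What is collected.** Protocol 6.4 records admission MAP, lactate and "dose of norepinephrine and dobutamine", and a SOFA score.

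**The concern.** A variable belongs in an imputation model when it predicts both the outcome and whether the outcome is seen. The protocol's own rationale (4.3) links the circulation to both: MAP to cerebral saturation, and mean MAP and SVO₂ in range to survival (odds ratios 3.72 and 10.32). Those are values during the ICU stay rather than at admission, but they place the circulation on the trial's central causal path. The intervention acts on that path, so it could change which patients in shock reach the scanner. If it does, and shock relates to ischaemia beyond what NSE, EEG and the other predictors capture, the missing-at-random assumption fails differently in the two arms and the primary difference is biased.

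**Working it through.** **1. Scale.** SD 8.9, 56 per group, 80% power and two-sided alpha 0.05 (Protocol 6.9.1) give a detectable difference of 8.9 × (1.960 + 0.842) × √(2/56) = 4.71 points (4.75 with the t distribution). A 40% reduction then implies a control mean of 4.71/0.40 = 11.8%. That mean is not stated, so 56 is consistent with it but cannot be verified. The 4.71 serves here only as a yardstick.

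**2. Model against data.** The SAP model has 4 baseline items, 5 NSE values, EEG, arm and death flag: 12 terms. None is lactate, MAP, vasopressor dose or SOFA.

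**3. Size of bias from the omission.** All inputs here are assumed: n = 112, 30% in shock, true difference −4.7, shock raising the endpoint by 3 or 6 points. The model already holds arm, a neurological marker and 7-day death. Entries are bias in the difference, from 4,000 replicates with regression imputation; negative means the benefit is overstated.

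| Shock effect | Missing among shock patients, control/intervention | Without shock term | With shock term |
|---|---|---|---|
| 3 | 50%/50% | −0.03 | −0.03 |
| 3 | 40%/60% | −0.14 | 0.02 |
| 3 | 30%/70% | −0.37 | −0.04 |
| 6 | 50%/50% | 0.02 | 0.02 |
| 6 | 40%/60% | −0.38 | −0.04 |
| 6 | 30%/70% | −0.62 | 0.05 |

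Under unequal missingness this is 0.14/4.7 = 3% to 0.62/4.7 = 13% of the assumed effect; the largest is about a third of the estimate's standard deviation (0.62/1.87). Swapping the arms reverses the sign. If the treatment effect is also halved in shock patients, the bias at 30%/70% is −0.70 to −1.11 without the term and −0.29 to −0.37 with it.

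A large-sample version without the death flag (SD 8.9, difference 4.75, about 30% missing) gave 0.04 to 0.3 points at 25% versus 35% missing. It gave 0.2 to 0.9 if missingness also depended more on shock in the intervention arm, and at most 1.1 at 20% versus 40%.

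**4. The death flag.** Anyone who dies before the day 4-5 scan also dies within 7 days, so every such patient carries the flag. Its coefficient can be estimated only from flagged patients who were scanned, that is, who lived to the scan and died afterwards. Protocol 6.7 keeps full ICU treatment to at least day 5 with two narrow neurological exceptions, so those later deaths plausibly include many neurological withdrawals. Circulatory deaths before the scan then borrow high ischaemia values. Omitting shock pushes their imputed values too low, so the two errors partly offset.

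Simulations in which pre-scan death follows shock and later death follows brain injury (inputs assumed) show this:
- Flag dropped: adding shock cut the bias from as much as 0.66 to about 0.02.
- Flag kept: bias was 0.24 to 0.42 with shock added, against 0.04 to 0.34 without, and worse in 15 of 16 unequal-missingness scenarios. A second set left about 0.5 to 0.7 and was worse in all 12.
- Flag kept, later deaths unrelated to brain injury: adding shock removed the bias.

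**5. Precision at trial size.** With n = 112, 31-33% missing, the 12 SAP-type terms and three circulatory terms added, the estimate's SD changed by −0.02 to +0.02 and its root mean square error by −0.04 to +0.03, around a standard error near 2.0. Bias without the added terms was at most 0.36.

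**The case against.** The SAP recognises the missing-data problem and prespecifies imputation with neurological and mortality predictors. The bias is conditional: it vanishes if missingness works the same way in both arms, it shrinks to the extent that shock correlates with NSE, EEG or rhythm, and in most scenarios it is small against a standard error near 2 points. All of that stands. It makes this an improvement to the model and not a demonstrated error.

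Stronger readings are tempting but not supported:
- *Support devices cause missing scans.* Protocol 6.5.1 says "placement of an IABP will be considered in the catheterization laboratory" in the intervention arm, and 6.3.2 excludes "MRI incompatible cardiac or neurosurgical device" at entry. No passage says that a balloon pump prevents the MRI or is still in place on day 4-5. The balloon-pump ratio is recorded for all patients where applicable, so use in one arm only is not established.
- *Early deaths leave nothing but baseline items.* NSE is taken daily from day 0 to 5 and the EEG item is from day 1, so a patient who dies on day 1 may have both.
- *Circulatory terms make the imputed values more precise.* At n = 112 no gain is seen.
- *Adding the terms removes the bias.* This fails when the 7-day flag is kept and later deaths are neurological.

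Nor is the eligibility criterion at fault. It shows only who is enrolled; the choice at issue is in SAP 7.4.

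**Conclusion.** The gap is real and cheap to close. The SAP leans on imputation for a substantial share of the primary endpoint and leaves out recorded severity measures on the pathway that the intervention targets. The likely effect on the primary difference is between zero and a few tenths of a point. It reaches about 1 point only under strong assumptions: markedly different missingness by arm together with effect modification by shock, or dependence on shock that is much stronger in one arm. The documents give no missingness rates, no proportion in shock and no shock-outcome relation, so the size cannot be fixed from them. A reader might infer that a large part of the treatment effect is at risk; that rests on the extreme inputs alone. The 7-day death flag must be handled together with the new variables.

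**What to change.** Before unblinding, amend SAP 7.4 and 10.1:

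1. Add admission lactate, admission norepinephrine dose and SOFA to the imputation model. Protocol 6.4 does not state when SOFA is scored, so specify the admission value only. Leave the primary ANOVA unchanged.
2. Repeat the imputation without the 7-day death flag, or with deaths before the scan separated from deaths after it. In the separated version no scan is observed for pre-scan deaths, so their offset must be assumed and varied.
3. Tabulate missing MRIs by arm and reason (death before the scan, haemodynamic instability, other). The SAP's summaries already give non-missing counts and deaths by arm; only the reasons are new.
4. State whether the new variables also enter the survival model in SAP 10.2.3, which takes its baseline covariates from 7.4.

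Cost: SAP wording, one extra imputation run, and three terms on top of 12, fitted on roughly 70 to 90 scanned patients (112 less about 20% to 38%, an assumed range). No new data are needed, the sample size does not change, and little change in precision is expected.

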2. ETHICS

2.1. Independent Ethics Committee (IEC)

The protocols and local Informed Consent Forms must be reviewed and approved by each of the participating institution's Independent Ethics Committee (IEC) prior to the initiation of patient accrual. The IEC must be notified of all subsequent protocol amendments. In addition, progress reports will be submitted to the IEC by the investigator as indicated by IEC's guidelines. Each IEC must meet the applicable regulatory requirements for composition, documentation, and operational procedures.

2.2. Ethical Conduct of the Study

The study will be conducted in accordance with the protocol, the principles that have their origins in the Declaration of Helsinki, as well as ICH GCP and applicable national and local regulatory requirements, including but not limited to the Belgian Laws of 7 May 2004 relating to experiments on the human person (LEH), of 22 August 2002 on Patients' Rights and of 8 December 1992 (as amended) regarding the Protection of Privacy in relation to the Processing of Personal Data. All essential documents will be archived.

2.3. Patient Information and Informed Consent

The informed consent will contain all elements required by ICH GCP. Written informed consent will be obtained from a next of kin prior to enrollment and participation of the study Subject. If a next of kin or another designated person is not available, a procedure for inclusion in the study in emergency situations will be applied. A definitive post hoc consent form will ultimately be obtained from patients who survived but had been initially treated on the basis of the emergency consent. Subjects or legally representatives will be informed of any significant new finding developed during the course of the research that may affect their decision to continue participation.

The Study Centers shall use the informed consent forms as approved by the appropriate ethics committee. The Study Centers further commit to conduct the study only on the basis of prior written consent by the Subjects or their legal representatives. The Study Centers shall retain such informed consent forms in accordance with the applicable regulatory requirements.

3. INVESTIGATORS AND STUDY ADMINISTRATION STRUCTURE

3.1. Investigators

Two sites (ZOL-Genk and UZ Leuven) will participate in the trial.

3.3. Study Coordinating Centre

The Leuven Coordinating Centre (LCC) will provide services with respect to the design and operation of the clinical trial. LCC will interact closely with the Principal Investigators and will have operative responsibility for different areas like regulatory submissions, randomization, data management and safety reporting.

3.4. Data Monitoring Committee (DMC)

A Safety and Data Monitoring Board will be established to provide independent oversight to this trial. The primary responsibility of the DSMB will be to review the progress and conduct of the trial in order to maintain scientific rigor and to ensure the well being of patients participating in the trial. Data will be provided to the DSMB after inclusion of the 60th patient. The DSMB consists of [name] (MD, Chair), [name] (MD) and [name] (MD).

4. INTRODUCTION

4.1. The clinical problem

There is absolutely no doubt that sudden cardiac death is a major problem in Belgium in terms of numbers of patients, medical impact and socio-economic impact. Each day, approximately 30 adults suffer from an unexpected out-of-hospital cardiac arrest in Belgium, a number exceeding the incidence of breast or prostate cancer with an estimated 25 new patients per day in Belgium. In addition, many cardiac arrest patients are young (mean age in our hospital 60±12 years, 56% of patients younger than 65 years) with a large economic potential for society. In the community, the occurrence of sudden death often takes center stage through highly mediatised cases of cardiac arrest in young sportsmen with or without a previously undiscovered cardiac anomaly. Apart from the traumatic experience of these dramatic sudden events, only 40% of patients that reach the hospital with spontaneous circulation survive without major neurological impairment or care dependency. An additional 5-10% of the cohort survives with major neurological impairment including a permanent vegetative state. These sobering outcome data and the large economic burden for society (estimated cost of a nursing home facility for these patients approximately 30-50000 €/year) mandate novel treatment strategies that could improve prognosis after cardiac arrest.

Apart from temperature management to avoid fever, no single in hospital randomized controlled intervention trial has improved outcome of these patients. In this way, there is absolutely no doubt that a positive result of the Neuroprotect post-CA trial would be a clear added value for this vulnerable and highly under-investigated patient group.

